12.0 DATA REPORTING / REGULATORY CONSIDERATIONS

Adverse event lists, guidelines, and instructions for AE reporting can be found in Section 7.0 (Adverse Events and potential risks).

12.1 Data Reporting

The REDCap database will be utilized, as required by the Montefiore/Einstein Cancer Center, to provide data collection for both accrual entry and trial data management. REDCap is a Clinical Trials Management System housed on secure servers. Access to data through REDCap is restricted by user accounts and assigned roles. Once logged into the REDCap systems with a user ID and password, defined roles for each user limit access to appropriate data. User information and password can be obtained by contacting the REDCap administrator. REDCap is designed with

the capability for study setup, activation, tracking, reporting, data monitoring and review, and eligibility verification. This study will utilize electronic Case Report Forms. A calendar of events and required forms will be available on REDCaps.

12.2 Regulatory Considerations

The study will be conducted in compliance with ICH guidelines and with all applicable federal state or local laws.

12.2.1 Written Informed consent

Provision of written informed consent must be obtained prior to any study-related procedures. The Principal Investigator will ensure that the subject is given full and adequate oral and written information about the nature, purpose, possible risks and benefits of the study as well as the subject's financial responsibility. Subjects must also be notified that they are free to discontinue from the study at any time. The subject should be given the opportunity to ask questions and be allowed time to consider the information provided.

The original, signed written Informed Consent Form must be kept with the Research Chart in conformance with the institution's standard operating procedures. A copy of the signed written Informed Consent Form must be given to the subject. Additionally, documentation of the consenting process should be located in the research chart.

12.2.2 Subject Data Protection

In accordance with the Health Information Portability and Accountability Act (HIPAA), a subject must sign an authorization to release medical information to the regulatory authority, or Institutional Review Board access to subject's medical information that includes all hospital records relevant to the study, including subjects' medical history.

12.2.3 Retention of records

The Principal Investigator will supervise the retention of all documentation of adverse events, records of study drug receipt and dispensation, and all IRB correspondence for as long as needed to comply with local, national and international regulations. No records will be destroyed until the Principal Investigator confirms destruction is permitted. Records will be retained for 5 years after the last accrual.

12.2.4 Audits and inspections

The Montefiore Einstein Cancer Center Cancer Clinical Trials Office (MECC CCTO) quality assurance team will perform monitoring visits and audits of regulatory documents and participant charts either in person or remotely for all sites which includes but is not limited to eligibility verification, drug accountability, and source data verification. The MECC quality assurance team will follow the MECC DSMP timeline of quality assurance program monitoring and audit frequency based on the protocol risk category.

The purpose of an audit or inspection is to systematically and independently examine all study-related activities and documents to determine whether these activities were conducted, and data were recorded, analysed, and accurately reported according to the protocol, Good Clinical Practice (GCP), guidelines of the International Conference on Harmonization (ICH), and any applicable regulatory requirements.

13.0 STATISTICAL CONSIDERATIONS

The combination of HMA (decitabine or azacytidine) and Venetoclax are approved to treat elderly patients with AML. The FDA-approved regimens of HMA/venetoclax is with pulse-cycle drug administration of HMA and venetoclax requires continuous dosing. However, with this approach the myelosuppression from treatment leads to frequent dose-reductions, and/or cycle delays especially for many older patients and patients who have poor bone marrow reserve. In addition, some subgroups of myeloid malignancies have not been shown to benefit from standard dosing of decitabine/venetoclax as outlined above in section 1 study rationale. The registration trial which lead to FDA approval of Azacitidine in combination with venetoclax (VIALE-A) used standard dosing (Aza 75 mg/m² days 1-7, venetoclax 400 mg days 1-28 of a 28 days cycle). In this trial 24% of patients had to discontinue azacitidine–venetoclax due to adverse events and more importantly the dose interruption of azacitidine–venetoclax between cycles owing to adverse events occurred in 72% of patients.

While venetoclax enhances the activity of HMA, the inability to get the required doses due to myelosuppression limits the benefits. Our hypothesis is that the weekly low dose venetoclax/decitabie regimen avoids severe myelosuppression by preserving functional hematopoietic cells, while maximizing suppression of clonal cell population by decitabine's S-phase dependent DNMT1-targeting while the venetoclax priming inhibits de novo pyrimidine synthesis which counters a major mechanism of resistance to decitabine in myeloid malignancies. This regimen will allow for continuous dosing without interruptions due to myelosuppression and may

lead to more durable responses. The doses and total amounts of decitabine/venetoclax administered in this trial are known to be safe and effective in this patient population based on our experience at Montefiore medical center using this regimen. Therefore, in this proof-of-concept study, the primary end-point relates to the ability to administer the treatment continuously without interruptions compared to standard dosing used in VIALE-A trial

Considerations in choice of primary end-point: The primary end-point is the overall percent of patients who can receive weekly low dose decitabine/ven during the induction period (weeks 1-12) without dose interruptions. The reason for the 12-week time period was used is because responses to HMA/ven are gradual and more so with the low dose regimen. For example, in VIALE-A, the median time to first response (either complete remission or complete remission with incomplete hematologic recovery) was 1.3 months (range, 0.6 to 9.9) and 2.8 months (range, 0.8 to 13.2), respectively.

Considerations in sample-size calculations: As mentioned above, in VIALE-A dose interruptions were required in 72% of patients receiving standard currently approved dosing of Aza/ven. Therefore, the sample size has been calculated to detect a 50% reduction in treatment interruptions, which would suggest that the proposed regimen has a high likelihood of being an advance over the current FDA approved regimen.

Sample size calculations: A Simon 2-stage Optimal design is used to test the null hypothesis of 60% or more patients requiring a dose reduction versus the alternative hypothesis of 36% or less of patients requiring dose interruptions with a one-sided alpha of 5%, power of 80%, and a probability of early termination of 0.77. After assessing dosing of decitabine/ven in 13 patients in the first stage, the trial will be terminated if 7 or more patients require dose reduction. If the trial goes on to the second stage, a total of 33 patients will be studied. If the total number of dose reduction is greater than or equal to 16, the treatment regimen is rejected.

After the 19 patients were enrolled into the study and 17 patients were evaluable after a 12-week induction, there were with no safety concerns. If after a total of 33 patients have been evaluated after the 12-week induction period and show satisfactory results (i.e., fewer than 16 dose reductions during the induction period, so the treatment was not rejected), the proposed amendment for an expansion phase will be implemented in which additional patients will be enrolled to gather more data on the secondary endpoints of efficacy using this regimen in MDS and AML. Background for the rationale for this amendment is outlined in section 1.4. Given the early efficacy seen in the first 11 evaluable patients with AML (64% response rate) and very low toxicity, more subjects will be required to establish the secondary

endpoints of efficacy in MDS and AML. This additional data may help in the design subsequent studies which will require adding an additional agent to this regimen as a backbone as it's becoming increasingly clear the HMA/VEN does not have a cure rate²⁵ and the way forward will require a third effective agent with multiple trials now evaluating triplets and using HMA/VEN as a backbone. The comparator arm for HMA/VEN in all trials is the current standard of single agent HMA (Azacitidine or Decitabine).

The expansion phase will be stratified by disease type, i.e., MDS and AML.

Single agent HMA has a 16% CR rate in MDS.²⁶ The CR rate with HAM/VEN is expected to be at least 36%. The target sample size for the MDS group will be a total of 32 patients (from both initial and expansion phases). With this sample size, we can estimate the CR rate with standard error no greater than 9%.

In AML, single agent HMA has a CR rate of 17.9%.¹ The CR rate with HAM/VEN is expected to be at least 38%. With a total of 38 AML patients from both phases, we can estimate the CR rate with standard error no greater than 8%.

In summary, an amendment will be added for additional 42 patients (above the originally planned 33 patients) with either MDS or AML after accounting for drop-outs. For example, if we assume among the first stage of 33 patients, we have 16 MDS, 17 AML, then the study needs enroll additional 16 MDS and 21 AML, a total of 37 patients. Allowing up to 5 patients to drop out from the study and the study may also enroll approximately 10 patients with other rare myeloid malignancies such as CMML and MDS/MPN. We therefore expect the total number of patients needed to be enrolled in the study to be not more than 85 (33+37+5+10) patients.

Safety: Incidence of treatment-emergent adverse events will be tabulated severity/grade, and whether the AE resulted in death or discontinuation of treatment.

Early Stopping Rule for Excessive Toxicity in Expansion Phase: We will continue using Bayesian toxicity monitoring in the expansion phase, similar to what was described in the initial stage of the study (Sec 6.6), to allow for early stopping due to excessive toxicity.

Laboratory data will be summarized in tables that show changes from pre-treatment values and frequencies of abnormal values. Descriptive statistics will also be provided.

Efficacy: The primary end-point of a decrease in dose interruptions will be described as proportion of patients point-estimates, together with the corresponding 95% confidence interval. Kaplan-Meier method will be used to summarize time to event variables.

Secondary end-points and scientific correlative studies: For the secondary end-points and scientific correlates (secondary objectives), either logistic regression or correlation analysis will be utilized to examine and assess the relationships and predictive nature of these biological parameters on hematologic improvement and ability of decitabine/ven to deplete DNMT1 in malignant cells, and the alteration of pyrimidine metabolism. Descriptive summaries of the data will be provided.

Accrual rate: Estimated accrual rate of 1-3 patients per month with approximately 18-24 months to meet total accrual goals, and additional 3 months to observe primary outcome measures. DOR of response will be followed for up to two years, thus a total of three to four years is anticipated to meet all study endpoints.

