Rationale	
Noncytotoxic dosing of decitabine given weekly at a dose of 0.2 mg/kg induces depletion of DNA methyltransferase 1 (DNMT1) while minimizing the toxicity and myelosuppression seen with standard HMA dosing regimens. This approach has been shown to be effective in a wide spectrum of patients with myeloid malignancies, including patients with resistant disease such as P53 mutations.
 
Preclinical studies have demonstrated that adding a dose of venetoclax prior to administering decitabine enhances the anti-leukemic activity of HMAs by inhibiting de novo pyrimidine synthesis, which is a major mechanism of resistance to HMA in MDS/AML. Decreasing the dose of venetoclax to a weekly schedule also spares normal myelopoiesis. Therefore, a weekly dosing of decitabine/venetoclax is a very attractive option for a patient population who cannot tolerate or are not known to benefit standard Aza/ven.

Primary Objective	
Primary Endpoint
 
Percentage of participants who are able to continue on treatment without dose interruptions or delays. Defined as delaying or interrupting treatment due to toxicity or intolerance during the induction phase (weeks 1-12)

Secondary Objective(s)	
Secondary Endpoints: (1) Cumulative incidence of response for both CR, CRI and overall response; (2) Event free survival

	
(EFS); (3) Complete remission or complete remission with partial hematologic recovery rate (CR+CRh); (4) Post baseline transfusion dependence rate; (5) Fatigue/quality of life (QoL); (6) Rate of hospitalization; (7) Infection rate
 
Scientific Correlates:
 
Correlation of DNMT1 depletion with clinical response criteria

Sample Size	85 patients
Disease sites/Conditions	Myeloid malignancies: ≥MDS, AML, MDS/MPN overlap syndrome
• Interventions	
 • Venetoclax 400 mg po on days 1, 8, 15 and 28 of each cycle (28day cycle) (+/- 1 day allowed). • Decitabine 0.2 mg/kg SQ on days 1, 8, 15, 22 (for aggressive disease will add decitabine on days 2, 9, 16, 23)

TABLE OF CONTENTS

SUMMARY OF CHANGES	3
ABBREVIATIONS.....	5
STUDY SCHEMA	6
PROTOCOL SUMMARY	7
TABLE OF CONTENTS	9
1.0 INTRODUCTION	12
1.1 BACKGROUND.....	12
1.1.1 Diseases- Myeloid malignancies: Acute Myelogenous Leukemia (AML) and Myelodysplastic Syndromes (MDS) and Myeloproliferative neoplasms (MPN).....	12
1.1.2 Treatment of myeloid malignancies	12
1.2 STUDY RATIONALE.....	14

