1.2 Study Rationale

1.2.1 Rationale for low dose non-cytotoxic weekly Decitabine dosing:

Decitabine is a nucleoside analogue which depletes the epigenetic regulator DNA methyltransferase 1 (DNMT1). It is routinely dosed in myeloid malignancies to generate dose-dependent DNA damage in malignant cells that then triggers apoptosis (cytotoxicity). However, with this approach normal dividing hematopoietic cells are unfortunately also simultaneously destroyed causing prolonged cytopenia's and the myelotoxicity that result from it. In fact, in the VIALE-A trial where “standard” myelotoxic doses of HMA/ven were combined, 24% of patients had to discontinue treatment due to adverse events and more importantly 72% of patients required dose interruptions between cycles due to adverse events.¹ While some patients can get an initial response to high doses of HMA/ven, dose interruptions decrease the durability of many responses. An approach of continuous drug exposure for suppression of clones which spares preserved non-clonal hematopoietic stem cells may allow continuous dosing without interruptions due to cytoopenias and may lead to more durable remissions.

Weekly low doses of Decitabine administered as a subcutaneous injection has been shown to cause on target DNMT1-depletion (even cytoreduce p53-null myeloid malignancies) while sparing normal hematopoiesis. Saunthararajah et al identified the minimum doses of decitabine (0.1–0.2 mg/kg) can cause molecular targeted DNMT1 depletion via terminal differentiation, instead of apoptosis, while sparing normal hematopoiesis by limiting the off-target anti-metabolite effects/cytotoxicity.^{3,4} These doses are given 1–2 times a week to increase S-phase dependent DNMT1-depletion. Long term followup (up to 6.5 years) using this approach (weekly SQ decitabine of 0.1-0.2 mg/kg), has demonstrated durable responses in myeloid malignancies across the clinicopathologic spectrum of diseases which include MDS, MDS/MPN overlap, MPN or AML, which is not surprising given the ability to continue weekly dosing without dose interruption due to

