- Venetoclax can also cause cytopenias but less so with once weekly dosing. If cytopenias are thought to be due to venetoclax, can first decrease dose by 50% (200 mg daily) and if cytopenias persist and is thought to be due to venetoclax, hold venetoclax and continue decitabine single agent. Can restart venetoclax based on the clinical judgment of the treating physician

6.1.5 **Adjustments for non-hematologic toxicity \geq Grade 3**

Low doses of decitabine and weekly venetoclax have low risk of renal toxicity, and are not felt to be renally toxic. There is concern that decitabine has hepatotoxicity at standard dosing, but risk should be nominal in the setting of very low doses. In general, workup for alternative causes for non-hematologic toxicity should be strongly considered, and decitabine and venetoclax is only dose reduced in the absence of alternative explanation. However, doses should be reduced for toxicity considered *at least possibly related* to decitabine and venetoclax. This includes laboratory abnormalities.

Infections in patients with myeloid malignancies are common and should be treated accordingly. Infections do not require dose adjustments unless there is clear evidence of relation to decitabine or venetoclax toxicity leading to the associated infection. In other words, most infections should not warrant dose modification.

Table 1: Adjustments for non-hematologic toxicity

Serum creatinine (Renal Toxicity)	
If pretreatment creatinine is < 0.5, and increased in creatinine to ≥ 1.5
 
If pre-treatment creatinine 0.6-0.8 mg/dL, an increase to ≥ 1.7 mg/dL
 
For pretreatment creatinine of 0.9 to 3.0, and a doubling of creatinine, or > 5.0.
	
If no alternative cause identified and toxicity felt at least possibly related, hold decitabine and venetoclax until recovered below threshold and restarted with a 25% dose reduction. Can go back to full dose when felt safe to do so by treating physician.
 
If toxicity recurs after dose reduction without an identifiable alternate cause and is thought to be related to decitabine or venetoclax, patient should be removed from protocol

-----------------------------------	--	--

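### The 72% VIALE-A benchmark and the undivided 12-week endpoint are not like for like and the 60% null has no derivation, so passing the Simon rule does not by itself show an improvement on standard aza/ven

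*Combined protocol and SAP*

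**What the plan says.** The sample-size considerations in section 13.0 start from the statement that "in VIALE-A dose interruptions were required in 72% of patients receiving standard currently approved dosing of Aza/ven". Section 13.0 describes the reference event in VIALE-A as dose interruption "between cycles owing to adverse events occurred in 72% of patients". Section 1.2.1 says the same: "72% of patients required dose interruptions between cycles due to adverse events". Neither place gives a time window or says whether the adverse events had to be drug-related.

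The Protocol Summary gives this trial's event as "Defined as delaying or interrupting treatment due to toxicity or intolerance during the induction phase (weeks 1-12"). Two other sections narrow it: section 2.1 counts only delays or interruptions longer than two weeks, and section 3.0 refers only to interruptions due to cytopenias. Sections 6.1 and 6.1.4 discourage holds during the same 12 weeks.

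Section 13.0 presents the primary endpoint as a comparison with VIALE-A dosing and aims to detect a halving of interruptions. It says such a result would suggest a high likelihood of an advance over the approved regimen. The design is Simon two-stage: null 60% or more, alternative 36% or less; stop at 7 or more events in 13; reject the regimen at 16 or more in 33.

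**The concern.** A single-arm test controls error against the null rate and nothing else. To say something about standard aza/ven, the null must be a credible lower bound for what standard aza/ven would show on the same event over the same time. Here the reference and the endpoint differ in window, in cause and, under section 2.1, in minimum duration. The discouragement of holds in weeks 1-12 may lower the count further. The plan neither aligns the two measures nor explains the step from 72% to 60%.

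At stake is the interpretation of a pass. If standard aza/ven has a 12-week rate on this definition that is clearly below 60%, a pass is weaker evidence against it than the nominal 5% suggests.

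**Working it through.** **Inputs.** From section 13.0: benchmark 72%; null event rate 60%; alternative 36%; first stage 13 patients, stop at 7 or more events; total 33, reject at 16 or more; one-sided error 5%, power 80%, early-termination probability 0.77. From section 1.4 (rationale for cohort expansion): 1 interruption among 17 evaluable patients.

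**Step 1: reproduce the design.** Let q be the true event rate and let a success be a patient with no event, with probability 1 − q. The trial continues with 7 or more successes in 13 and passes with 18 or more in 33.

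P(pass | q) = Σ over k = 7 to 13 of P(X₁ = k) × P(X₂ ≥ 18 − k), with X₁ ~ Bin(13, 1 − q) and X₂ ~ Bin(20, 1 − q).

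- q = 60%: error 0.0474; early termination 0.771.
- q = 36%: power 0.809.

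All agree with the plan. A search over designs returns the same Simon optimal design.

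**Step 2: the role of each number.** 0.5 × 72% = 36%, so the 72% fixes the alternative only. The tested null is 60%, from which 36% is a 40% relative reduction (1 − 36/60). The rule can also be passed with 15 events in 33, an observed 45.5%. Set against 72%, that is a reduction of 1 − 45.5/72 = 37%, so a pass does not require a halving.

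**Step 3: chance of passing by true rate on this trial's event.**

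| True rate | P(pass) |
|---|---|
| 72% | 0.1% |
| 65% | 1.2% |
| 60% | 4.7% |
| 55% | 13% |
| 50% | 28.5% |
| 45% | 48% |
| 40% | 68% |

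The probability reaches 5% at a rate of about 59.8%, and 59.8/72 = 0.83. If less than about 83% of the 72% would count under this trial's window and definition, the error against standard aza/ven exceeds 5%.

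**Step 4: how the window might matter (assumptions, not estimates).** The documents do not say when the VIALE-A interruptions occurred. They give median times to first response there as "1.3 months (range, 0.6 to 9.9) and 2.8 months (range, 0.8 to 13.2), respectively", so observation ran past 12 weeks.

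- Constant per-cycle rate, with 72% reached over T cycles: the 12-week rate is 1 − 0.28^(3/T). T = 3 gives 72% (pass 0.1%), T = 5 gives 53% (17%), T = 6 gives 47% (40%). The rate equals 60% at T = 3 × ln 0.28 / ln 0.40 = 4.17 cycles.
- Front-loaded: if 85% or 90% of the interrupted patients had their first interruption within three cycles, the rate is 0.85 × 72% = 61% or 0.90 × 72% = 65%, and the pass probability is 3.5% or 1.3%.

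The answer moves from well under 5% to well over it on an input that the documents do not supply.

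**The case against.** The strongest case for the plan has five parts.

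**The null already has a margin.** It sits 12 points below 72%. A regimen with a true 72% rate passes with probability 0.08%, and early clustering of interruptions keeps the error within 5%. This stands, but the plan does not say that the margin was meant to absorb the differences in window and definition, or show that it is enough.

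**Some differences may push the other way.** The benchmark counts interruptions between cycles. This trial doses weekly, and section 1.4 reports a single held dose as an interruption, which may be a broader event. The target population is also described as unable to tolerate, or not known to benefit from, standard dosing, so its rate on standard dosing could exceed 72%. This stands, and the net direction is not established.

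**The wording is hedged.** This is a pilot, the plan says only that the result would suggest a likely advance, and section 13.0 reports a proportion with a 95% confidence interval. The hedge is fair to note, but the inference still rests on the unmatched figure.

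**Stronger readings are not supported.** A reader might infer that 72% is a whole-trial, any-cause rate, and that standard aza/ven would probably pass. The documents state neither a window nor an attribution rule, and long response times do not date the interruptions. A reader might also infer from section 6.1.5 ("Infections do not require dose adjustments unless there is clear evidence of relation to decitabine or venetoclax toxicity") that infection holds leave the count. That sentence governs dosing, not endpoint counting, and the Protocol Summary wording does not expressly require a judged drug relationship.

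**Changing the test now is hard to defend.** With 1 event in 17 known, failure would need at least 15 events in the next 16. Redefining the event or the null at this point would be a post-hoc change. This stands and shapes the fix.

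**Conclusion.** The point holds as a gap in justification, not as an arithmetic error. The 5% error is valid against a true rate of 60% or more on the trial's own 12-week event. The documents do not show that standard aza/ven lies there, and the false-pass risk is 4.7% at 60%, 28.5% at 50% and 48% at 45%. These figures are exact given the rate. Which rate applies is unknown, and a claim that standard aza/ven would itself pass goes beyond the documents. A pass therefore does not by itself support a halving of interruptions or an advance over the approved regimen.

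The interim 1/17 (exact 95% upper limit about 29%) makes a pass likely, so its interpretation matters more. That result comes from patients who completed 12 weeks, with holds discouraged and with section 3.2 providing for replacement of patients who stop for toxicity.

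Severity: should fix. Confidence: moderate, because the size and direction of the mismatch cannot be settled from the documents.

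**What to change.** 1. Leave the Simon rule, the 60% null and the sample size unchanged, because interim results are known.
2. State in section 13.0 that the primary test can show only a 12-week rate below a fixed 60%. Remove the inference of a 50% reduction and of an advance over the approved regimen, unless a 12-week, same-definition rate for standard dosing is cited. The contemporaneous standard-dose cohort described in section 1.4 is a possible source.
3. Reconcile the event wording in the Protocol Summary and sections 2.1, 3.0 and 13.0 (where the Simon rule is worded as dose reductions), so that the 60% refers to one defined event.
4. Add a descriptive analysis: cumulative incidence of first hold or delay of either drug for any adverse event, whatever its attribution, at 3, 6 and 12 months. Set that curve, not the 12-week proportion, beside the 72%, and note that the VIALE-A window is not stated.

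The cost is a few sentences in section 13.0 and one extra table. The comparison with 72% may look less favourable.

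### Section 13.0's stopping, rejection and expansion rules count dose reductions, while the primary endpoint is dose interruption, which is itself described inconsistently

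*Combined protocol and SAP*

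**What the plan says.** Section 13.0 (sample size calculations) states a single test that contains two events: "null hypothesis of 60% or more patients requiring a dose reduction versus the alternative hypothesis of 36% or less of patients requiring dose interruptions". The operative rules all use the event in the null. At stage 1, with 13 patients, "the trial will be terminated if 7 or more patients require dose reduction". At 33 patients, "If the total number of dose reduction is greater than or equal to 16, the treatment regimen is rejected". The expansion phase opens on satisfactory results, explained as "fewer than 16 dose reductions during the induction period, so the treatment was not rejected".

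Everything that gives these rules their meaning concerns interruptions. Section 13.0 defines the endpoint as "the overall percent of patients who can receive weekly low dose decitabine/ven during the induction period (weeks 1-12) without dose interruptions" and says that "the sample size has been calculated to detect a 50% reduction in treatment interruptions". The benchmark is interruption "between cycles owing to adverse events occurred in 72% of patients" (Section 13.0), or "72% of patients required dose interruptions between cycles due to adverse events" (Section 1.2.1). The Efficacy paragraph of Section 13.0 plans a proportion with a 95% confidence interval, again for interruptions.

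Four places describe the interruption, and they do not agree:

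| Place | Cause | Minimum length | Window | Population |
|---|---|---|---|---|
| Protocol Summary | toxicity or intolerance | none | weeks 1-12 | no restriction |
| Section 2.1 | toxicity or intolerability | more than two weeks | none stated | MDS and AML |
| Section 3.0 | cytopenias | none | none stated | no restriction |
| Section 13.0 | none stated | none | weeks 1-12 | no restriction |

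Section 13.0 may simply be shorthand for the Protocol Summary. Section 4.1 also admits CMML and MDS/MPN, which fall outside the population in Section 2.1.

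**The concern.** The null and alternative of one Simon test must refer to the same binary event per patient. Otherwise the stated alpha and power describe no real procedure. Here the null, both cut-offs and the expansion condition name one event. The alternative, benchmark, endpoint and estimate name another.

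The protocol does not use the two words as synonyms. Section 7.2.3 lists interrupted and reduced as separate actions to record. Section 1.4 (rationale for cohort expansion) reports one interruption and no reductions in the same 17 patients. Section 6.1 names holds and modifications separately for induction. Section 6.1.5.1 allows treatment to resume without a dose change, and Section 6.1.4 allows a venetoclax decrease with no stated hold. Table 1 in Section 6.1.5 couples a hold with a reduction at restart. The events therefore overlap, but neither contains the other. The final rule could also be read as a count of reductions rather than of patients.

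The conflicting definitions matter separately. Replacing the word reduction would still leave no single countable endpoint. On a weekly schedule, one missed dose can count under the Protocol Summary and not under Section 2.1. The choice could then be made after results are known, and the comparison with 72% would be hard to interpret.

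**Working it through.** **1. Reproduce the design for one event.** Inputs from Section 13.0: n1 = 13, stop at 7 or more; N = 33, reject at 16 or more; event rates 60% (null) and 36% (alternative); one-sided alpha 5%, power 80%, early termination 0.77. The 36% is half of the 72% benchmark (0.5 × 72% = 36%), so it is an interruption rate.

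With event rate p, the regimen passes if stage 1 has at most 6 events and the total is at most 15:

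P(pass) = Σ over x = 0 to 6 of Bin(x; 13, p) × P(Bin(20, p) ≤ 15 − x)

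- p = 0.60: 0.0474, the exact alpha (limit 0.05).
- p = 0.36: 0.8090, the power (stated 0.80).
- Early termination under the null: P(Bin(13, 0.60) ≥ 7) = 0.7712 (stated 0.77).

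A search over two-stage designs with N up to 44 returns this same design as optimal for 60% versus 36%. The arithmetic is sound, but only if one patient-level event is counted throughout.

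**2. Count the reported data under each wording.** Section 1.4 gives 17 patients who completed 12 weeks of induction, one of whom had a single dose held; there were no reductions. The cause of the hold is not given. Intervals are two-sided 95% Clopper-Pearson.

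- Any interruption in weeks 1-12 (Section 13.0): 1/17 = 5.9% (0.1% to 28.7%).
- Protocol Summary: 0 or 1 of 17, depending on whether the hold was for toxicity or intolerance.
- Section 3.0: 0 or 1 of 17, depending on whether it was for cytopenia.
- Section 2.1: cannot be determined. It has no window, and no data on holds after induction are given. Restricted to weeks 1-12 the count is probably 0, because one held weekly dose is unlikely to exceed two weeks. The denominator is also uncertain: 11 of the 17 are identified as AML, and the other 6 are not classified.
- Dose reductions: 0/17 (upper limit 19.5%).

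These are completers' figures, since Section 13.0 says 19 were enrolled. The outcome of the other two is not given. As an assumption, the any-interruption figure would run from 1/19 = 5.3% if neither had an event to 3/19 = 15.8% if both did.

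**3. Effect on decisions.** Stage 1 needed 7 events in 13. The reported total is 1 or 0, and at most 3 even if both remaining patients had an event, so the stop was not met under either word. For the final rule, 33 − 17 = 16 patients remain.

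- With 1 event so far, rejection needs at least 15 of 16: P(Bin(16, p) ≥ 15) = 0.0033 at p = 0.60 and 0.0377 at p = 0.72.
- With 0 so far, it needs all 16: 0.60^16 = 0.0003 and 0.72^16 = 0.0052.

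**4. Illustration with assumed rates.** If interruptions truly occurred at the 60% null but the rule counted reductions, the chance of passing would be 0.047, 0.48, 0.93 or 0.99 for reduction rates of 60%, 45%, 30% or 20%. None of these reduction rates is in the documents.

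**The case against.** The strongest reply is that this is a slip that any analyst would correct. A single test must have one event, and the endpoint paragraph, the benchmark, the target effect, the alternative and the planned estimate all say which one it is. The design reproduces exactly for that event, so nothing numerical changes. The interim data also leave no practical doubt about stage 1 and very little about the final rule.

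Most of that stands. Reduction is probably a slip, and no decision is shown to have gone wrong. But the word appears in the null, both cut-offs and the expansion condition, which are the only formal decision rules for the primary endpoint, so it should not be left to an analyst's inference.

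It can also be said that the Protocol Summary and Section 3.0 are short descriptions and that Section 2.1, as the stated objective, should govern. That does not settle the matter. Section 2.1 has no window, while Section 13.0 specifies weeks 1-12 and Section 6.4 places measurement of the primary endpoint at week 12. Its two-week threshold also appears in none of the other descriptions and is not part of the benchmark as the protocol reports it.

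**Conclusion.** The point holds. As written, every decision rule in Section 13.0 counts an event other than the primary endpoint, and that endpoint has no single definition. Of the two faults, the conflicting definitions are the one that reaches the reported result: the one known induction event counts, may count or probably does not count depending on the section used.

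Three stronger readings are tempting, and the documents do not support them.

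- A reader might infer that the sample size or error rates are miscalculated. They are not: for one patient-level event at 60% versus 36%, alpha is 0.047, power 0.809 and early termination 0.771.
- A reader might infer that the stop, final or expansion decision has been or will be wrong. On the reported data stage 1 was passed under either word. With one event in 17, a final rejection has probability 0.3% at a 60% rate and 3.8% at 72%.
- A reader might infer that counting reductions inflates the false-positive rate by a known amount. The illustration needs assumed reduction rates. Because a reduction can occur without a hold, even the direction of the error is not certain.

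The conclusion rests on the text of the protocol and on the summary of 17 completers in Section 1.4, which gives neither the cause of the single hold nor any later holds.

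**What to change.** In Section 13.0, replace dose reduction with dose interruption in the null hypothesis, both cut-offs and the expansion condition, and state that the count is of patients with at least one event. Keep 13 and 33 patients and the cut-offs of 7 and 16.

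Reconcile the Protocol Summary and Sections 2.1, 3.0 and 13.0 to one endpoint with a single cause, minimum duration, weeks 1-12 window and population. Use that population for the counts of 13 and 33.

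The sponsor should justify the choice against the benchmark. The Protocol Summary wording is closest, because the benchmark is described as interruption due to adverse events with no stated minimum length. The match is not exact: the benchmark is between cycles and is not limited to 12 weeks, and the protocol should say so.

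Make the change in a dated amendment that discloses that interim results had been seen in this open-label study.

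The cost is wording and a recount. For actions tied to adverse events, Section 7.2.3 already requires interruptions and reductions to be recorded separately. The downside is that the observed event rate may be higher than under the reduction or two-week wording.
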